## 2.6 CV301 Next Generation Product Following PANVAC

Given the potential risks associated with the replicating capacity of the vaccinia-based PANVAC-V construct, the next generation cancer immunotherapeutic candidate, MVA-BN-CV301, was generated by Bavarian Nordic. It constitutes a recombinant non-replicating poxvirus-based immunotherapy derived from the MVA-BN construct. The new CV301 strategy

encodes the same 5 transgenes expressed by the previous PANVAC vector: CEA, MUC-1, B7.1, ICAM-1 and LFA-3. However, these inserts encode each of the transgenes with amino acid sequences that are slightly different from the original vectors. In fact, MUC-1 has been modified with additional agonistic epitopes. Consequently, the CV301 construct is expected to promote an antigen-specific targeted immune response for tumors expressing these antigens. In addition, a change in biosafety level also characterizes the new CV301 construct. Thus, whereas vaccinia possesses a BSL-2, MVA has been categorized as BSL1 in Europe. As well, similarly to the earlier PANVAC concept, CV301 also encompasses a heterologous prime-boost regimen employing MVA-BN-CV301 priming doses followed by Fowlpox-based FPV-CV301 boosting doses, thus replacing the former PANVAC-V and PANVAC-F components. Given the similarities between the CV301 and PANVAC vectors, the clinical development program designed for CV301 will rely on the extensive nonclinical and clinical data currently available from PANVAC.

In a first, still ongoing, BN-sponsored Phase 1 Trial of CV301 in Combination with Anti-PD-1 Therapy versus Anti-PD-1 Therapy alone in Subjects with Non-Small Cell Lung Cancer (CV301-2015-201), 12 subjects with various CEA/MUC-1 positive cancers were enrolled in the Phase 1a, 6 male and 6 female subjects, aged between 39 and 77 years. Of these 12 subjects, 3 received MVA-BN-CV301 at the lowest dose level, nominal  $4 \times 10^8$  Inf.U, 3 received the second dose level, nominal  $8 \times 10^8$  Inf.U, and 6 received the highest dose level, nominal  $1.6 \times 10^9$  Inf.U.

Initial safety data from Phase 1 of this trial involving 12 subjects dosed in three different dose levels show that the most frequently occurring treatment-related AEs were temporary and self-limiting, Grade 1 or 2 in severity and included injection site reactions (injection site erythema, pruritus, pain, induration and swelling) and general symptoms including fever/chills, flu-like symptoms, headache, fatigue/weakness, nausea/vomiting, myalgia and arthralgia. There was no occurrence of any of the pre-specified adverse events of special interest (immune-related events and cardiac events). There were no related SAEs. There were no dose limiting toxicities at all three investigated dose levels, so no maximal tolerated dose was identified. Based on this initial safety information, the selected dose level for the further course of the trial was nominal  $1.6 \times 10^9$  Inf.U (i.e. 4 injections of  $4 \times 10^8$  Inf.U in 0.5 mL) of MVA-BN-CV301.

## 2.7 Trial Population

The eligible population is based on the FDA approved indications of atezolizumab and the current standard of care; which includes: male and female subjects  $\geq 18$  years of age with locally advanced or metastatic UC, subjects will have mixed histologies that required having a dominant transitional cell pattern and locally advanced bladder cancer that is inoperable on the basis of involvement of the pelvic sidewall or adjacent viscera or bulky nodal metastasis. Metastatic subjects include Stage IV at first diagnosis and metastatic recurrences after locoregional treatments of earlier stages.

Bladder cancer subjects fit for first-line cisplatin are excluded because cisplatin-based combinations remain the standard treatment. The role of immunotherapy in this population is currently under clinical investigation but is not part of this clinical trial.

Two different cohorts of subjects with locally advanced or metastatic urothelial cancer are eligible for this trial: subjects with disease progression after first-line cisplatin-based chemotherapy, or candidates to second-line treatment. Five different antibodies targeting PD-1 or PD-L1 are currently approved in this indication and collectively have shown a better therapeutic index than the historical results achieved with chemotherapy agents. The second cohort is comprised of candidates to first line treatment but cisplatin-ineligible due to some of the following conditions: ECOG PS2, renal function impairment, hearing loss or peripheral neuropathy.

## **2.8 Risk/Benefit Assessment**

### **2.8.1 Potential Risks**

Considering that the novel MVA-BN-CV301 vector derives from the original MVA-BN construct and contains inserts already present in the PANVAC vector, its potential risks are based on the adverse reactions already reported for these two constructs. So far, within the MVA-BN clinical development program, more than 10,500 subjects have received at least one MVA-BN-based construct dose in completed and ongoing clinical trials, giving rise to a substantial database concerning the administration of MVA-based recombinant vaccines in different populations. These include healthy vaccinia-naïve, healthy vaccinia-experienced, HIV-infected subjects, subjects with atopic dermatitis and subjects with previous hematopoietic stem cell transplantation. In addition, the vaccinia-based PANVAC vector has been administered to approximately 450 subjects in different cancer indications. The main adverse reactions associated with both MVA-BN and PANVAC inoculation involve the development of local reactions at the injection site, e.g. erythema, pain, swelling, induration and short-lived flu-like systemic effects, ranging from mild to moderate intensity and resolving completely within the first seven days after vaccination. Additional risks potentially associated with MVA-BN-CV301 include fatigue, abdominal pain, nausea, and vomiting.

Despite the fact that the MVA-BN delivery vector constitutes a non-replicating, highly attenuated vaccinia viral strain, thorough cardiac monitoring protocols have been successfully implemented along the entire MVA-BN clinical development program. Similar safety measures were also carried out during clinical trials employing the replication-competent PANVAC and PROSTVAC-V constructs. No case of myocarditis, confirmed pericarditis, endocarditis or any other type of cardiac inflammatory disease (or related syndromes) has been reported to date for either of these products. However, several ischemic cardiac events and arrhythmias have been reported during PANVAC's clinical development program, particularly in pancreatic cancer subjects. In this regard, it has been shown that pancreatic cancer can induce severe nutritional and metabolic dysfunctions, thus facilitating different types of arrhythmias. Therefore, it seems

neither PANVAC nor MVA-BN-based therapies might induce any inflammatory cardiac events, as opposed to the early generation replicating smallpox vaccines like Dryvax® and ACAM2000®.

Furthermore, an additional series of potential risks associated with the current clinical trial protocol include those derived from blood and tissue sampling procedures. Blood draws may cause discomfort, bruising, light-headedness or fainting and rarely result in infection at the venipuncture site. Biopsy risk may include a small amount of bleeding, pain, swelling, bruising and possibly an infection. As well, similar to other vaccines, there is a risk of an allergic reaction or an anaphylactic event. Consequently, in order to offer appropriate treatment and supervision in case of a severe allergic reaction and/or dyspnea, 30 minutes' observation periods will be implemented by the trial site staff after each vaccination. Additionally, subjects with known severe allergies to eggs, egg products, or aminoglycoside antibiotics (for example ciprofloxacin, gentamicin or tobramycin) should be excluded from receiving MVA-BN-CV301.

The risks associated with atezolizumab are described in the package insert and may be expected during the use of atezolizumab in this clinical trial.

The risk derived from the combination of CV301 with the PD-1 inhibitors nivolumab and pembrolizumab is being studied in 'A Phase 1/2 Trial of CV301 in Combination with Anti-PD-1 Therapy Versus Anti-PD-1 Therapy Alone in Subjects with Non-Small Cell Lung Cancer' (CV301-2015-201, NCT02840994). No safety signal has emerged so far from this ongoing trial. Although the specific combination of CV301 with atezolizumab is being studied for the first time in this clinical trial, the drug classes to which these compounds belong has been previously combined and no safety concern is expected. As an example of a poxvirus-vectored therapeutic cancer vaccine combined with an immune checkpoint inhibitor we refer to the Phase 1 trial that studied PROSTVAC with ipilimumab ([Madan et al., 2012](#)).

## 2.8.2 Benefits

The expected benefit from CV301 used as a single agent is unknown. A randomized Phase 2 clinical trial comparing the use of the therapeutic cancer vaccine PANVAC in combination with docetaxel versus docetaxel alone showed a non-statistically significant trend in PFS in favor of the combination [7.9 months versus 3.9 months, HR=0.65, p=0.09] ([Heery et al., 2015](#)). Provenge® (Sipuleucel-T) is the first and only vaccine approved by the FDA and the clinical benefit observed in the pivotal clinical trial showed a unique pattern of OS prolongation without producing ORR nor PFS prolongation ([Kantoff et al., 2010a](#)). The recognition of this novel pattern of clinical benefit together with the observation of delayed responses triggered several initiatives to adopt new immunotherapy assessment criteria ([Hoos et al., 2010](#)). But results obtained with vaccines used as single agents may differ from results of vaccines used in combination.

The expected clinical benefit from PD-1/PD-L1 inhibitors has a different pattern. A relatively small fraction of subjects achieves durable ORR and this fact translates usually into prolonged

OS. PFS is often reported as negative, statistically nonsignificant and with no advantage observed in medians, but the tails of the Kaplan-Meier curves tend to separate with long-term follow up, which seems consistent with a durable benefit experienced by a relatively small fraction of subjects. The results reported from the pembrolizumab Phase 3 clinical trial in second-line UC ([Bellmunt et al., 2017](#)) fit well with this pattern repeatedly reported across various PD-1/PD-L1 inhibitors in multiple indications.

The expected clinical benefit pattern from the combination of CV301 with PD-1/PD-L1 inhibitors is uncertain at this moment. In this trial, ORR is selected as the key endpoint to capture the activity of the combination. Benefit is also expected in other endpoints, but OS and PFS are categorized as secondary endpoints. The safety information available on poxvirus-vectored vaccine justifies the expectation on CV301 contribution to therapeutic benefit without a substantial addition of toxicity.

### 3 Objectives

Refer to Trial Synopsis ([Section 1.4](#)).

## 4 Trial Design

### 4.1 Experimental Design

This is a Phase 2, single-arm, multi-institutional clinical trial designed to study the combination of CV301 with atezolizumab in the first-line treatment of UC not eligible for cisplatin-containing chemotherapy (Cohort 1) and in the second-line treatment of UC previously treated with standard first-line cisplatin-based chemotherapy (Cohort 2). The trial will be performed using an optimal two-stage design within each cohort ([Simon, 1989](#)). For the purpose of this trial, subjects are considered enrolled once they have received their first dose of trial product.

Stage 1, Cohort 1: Enroll 14 subjects. If objective response is not achieved in at least four subjects, the cohort will be stopped for futility. If objective response is achieved in at least four subjects, the cohort will proceed to Stage 2.

Stage 1, Cohort 2: Enroll 13 subjects. If objective response is not achieved in at least three subjects, the cohort will be stopped for futility. If objective response is achieved in at least three subjects, the cohort will proceed to Stage 2.

Stage 2, Cohort 1: Enroll an additional 19 subjects, such that a total of 33 subjects are available for the primary endpoint analysis.

Stage 2, Cohort 2: Enroll an additional 22 subjects, such that a total of 35 subjects are available for the primary endpoint analysis.

Further details of the two-stage design are in [Section 9](#).

## 4.2 Description of Trial Procedure

This trial will be conducted according to the schedule found in [Section 1.5](#) for ALL subjects. Visits should be scheduled within the intervals/visit windows given. Protocol waivers or exemptions are not allowed, apart from immediate safety concerns. Therefore, adherence to the design requirements including those specified in the Trial Procedure Schedule are essential and required for trial conduct.

### 4.2.1 Screening Phase

Patients identified as potential subjects in the trial will be provided with all the necessary information required to make an informed decision about their participation in the trial. At the conclusion of the informed consent process, subjects will be asked to provide written informed consent to participate in the trial by signing an ICF. This must be done before completing any protocol-specified procedures or evaluations (i.e., any procedures or evaluations not considered to be part of the subject's normal care). After signing the ICF, subjects will be evaluated for entry criteria during the Screening period within 28 days before administration of trial drug.

Subjects who fail the initial screening process may be re-screened up to 2 times. In the event of subject re-screening, the unique subject number assigned during the initial screening process should be used.

After written, informed consent, screening assessment will be performed. All screening assessments must be performed within 28 days prior to the first trial product. All screening labs should be performed within 14 days prior to the first trial product.

The following task will be performed at the Screening Visit:

- Demographics
- Medical History
- Physical Exam (PE) including vital signs\*
  - \*Blood pressure and pulse rate should be obtained after the subject has been seated in an upright position for at least 5 minutes
- ECOG
- Electrocardiogram (ECG)
- CT Scans of the thorax, abdomen and pelvis^
  - ^If there is a medical reason, subject may have MRI instead of CT scan upon approval from BN.
- Collection of concomitant medications
- Collection of adverse events after signing of informed consent
- Tumor biopsy\*\*

\*\*Subjects who do not have tissue specimens meeting eligibility requirements must undergo a biopsy sample collection during the screening period. Acceptable samples included core needle biopsies for deep tumor tissue (minimum three cores) or excisional, incisional, punch, or forceps biopsy samples for cutaneous, subcutaneous, or mucosal lesions).

- Blood samples for: (see [Section 8.2.7](#))
  - Hematology
  - Chemistry
  - Thyroid function test
  - INR, PT, aPTT
  - HIV, HBsAg, HCV
  - Biomarker analysis
- Urine sample for routine urinalysis (see [Section 8.2.7](#))
- Pregnancy test – either serum or urine test (for women of child-bearing potential)

Women and men of reproductive potential must consent to use of highly effective method of contraception at least 30 days prior to first dose of trial product and continue for 5 months after the last dose of atezolizumab (see Appendix 1, [Section 17.1](#)) and the method(s) used by each subject must be documented. This list does not apply to subjects with same sex partners or for subjects who are and will continue to be abstinent from penile-vaginal intercourse on a long term and persistent basis, when this is their preferred and usual lifestyle.

## 4.2.2 Active Trial Phase

After successfully passing the screening evaluations, the eligible subjects will enter the active trial phase starting with Visit 1-14.

### 4.2.2.1 Randomization

Not applicable. This is a single-arm, non-randomized clinical trial.

### 4.2.2.2 Visit Description

The following tasks will be performed at Visits 1-14.

- Targeted PE including vital signs\*
  - \*Blood pressure and pulse rate should be obtained after the subject has been seated in an upright position for at least 5 minutes
- ECOG
- Pregnancy test – either serum or urine test (for women of child-bearing potential)
- Review of concomitant medications
- Recording of AEs
- Blood samples for: (see [Section 8.2.7](#))

- Hematology
- Chemistry

In addition, at Visit 1:

- Thyroid function test
- First prime vaccination of MVA-BN-CV301\*\* and atezolizumab infusion.

\*\* The trial subject must be kept under close observation at the clinical trial site for at least 30 minutes following vaccinations

In addition, at Visits 2, 4, and Visits 6-14:

- Urine sample for routine urinalysis (see [Section 8.2.7](#))

In addition, at Visit 3, 4, 5, or 6:

- Tumor biopsy#

#Note: Biopsy is optional and can be performed at Visit 3, 4, 5, or 6.

In addition, at Visits 3, 5 and every 6 weeks through to Visit 14:

- Thyroid function test

In addition, at Visits 4 and Visits 7-14:

- CT scan of the thorax, abdomen and pelvis^  
^If there is a medical reason, subject may have MRI instead of CT scan upon approval from BN.

In addition, at Visits 2, 4, 7 and 10:

- Blood sample for biomarker analysis

In addition, at Visit 2:

- Second prime vaccination of MVA-BN-CV301 and atezolizumab infusion.  
\*\* The trial subject must be kept under close observation at the clinical trial site for at least 30 minutes following vaccinations

In addition, at Visits 3-14:

- Boost vaccinations of FPV-CV301 and atezolizumab infusion  
\*\* The trial subject must be kept under close observation at the clinical trial site for at least 30 minutes following vaccinations

Atezolizumab dosing visits: Every 3 weeks after Visit 6 through Visit 14

- Blood samples for: (see [Section 8.2.7](#))
  - Hematology
  - Chemistry
- Pregnancy test – either serum or urine test (for women of child-bearing potential)
- Review of prior/concomitant medications
- Recording of AEs
- Atezolizumab infusion

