## 1.4 Protocol Synopsis

Title	A Phase 2, Multicenter, Single-Arm Trial of CV301 in Combination with PD-1/L1 Blockade in Patients with Locally Advanced or Metastatic Urothelial Bladder Cancer
Clinical phase	Phase 2
Sponsor	Bavarian Nordic A/S 
Number of sites	Approximately 12
Vaccination dose, schedule and administration route	
Prime with MVA-BN-CV301 (nominal titer <math>1.6 \times 10^9</math> Inf.U) given subcutaneously (SC) on Day 1 and Day 22. One dose = four 0.5 mL injections. One injection = nominal titer <math>4 \times 10^8</math> Inf.U in 0.5 mL.
 
Boost with FPV-CV301 (nominal titer of <math>1 \times 10^9</math> Inf.U in 0.5 mL, given SC every 21 days for 4 doses (on days 43, 64, 85, and 106), followed by boosts every 6 weeks until 6 months on trial (i.e., days 148 and 190), then every 12 weeks until completion of 2 years. One dose = one 0.5 mL injection.
 
Atezolizumab fixed dose of 1200 mg intravenous on Day 1 of each 21-day cycle. No dose reduction permitted.

Trial duration	Approximately 104 weeks before starting the long term follow up.
Trial Population	
Patients with Locally Advanced or Metastatic Urothelial Cancer (UC) including bladder, ureter, renal pelvis and urethra.
 
Cohort 1: Ineligible for cisplatin-containing chemotherapy (first-line treatment)
 
Cohort 2: Previously treated with standard first-line cisplatin-based chemotherapy, PD-1/L1 Naïve (second-line treatment)

Number of Subjects:	Approximately up to 68
Primary objectives	Objective Response Rate (ORR; Complete Response [CR] + Partial Response [PR] Rate) as per Response Evaluation Criteria in Solid Tumors version 1.1 (RECIST 1.1)

Secondary objectives	Progression-Free Survival (PFS)  Overall Survival (OS)  Duration of Response  Safety of the treatment combination of CV301 with atezolizumab

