### 1.5 Trial Procedure Schedule

Trial Procedure	Screening Phase Day -28 to Day 1	Week (3 wk interval +/- 4 days)						Week (6 wk interval +/- 1 wk)		Week (12 wk interval +/- 2 wks)						Long Term FU	
		1	4	7	10	13	16	22	28	40	52	64	76	88	100 EOT 	3-month interval +/- 2 wks	
		Day															
		1	22	43	64	85	106	148	190	274	358	442	526	610	694 EOT		
		Visit															
		1	2	3	4	5	6	7	8	9	10	11	12	13	14		
Trial Procedures																	
Informed Consent 	X																
Demographics	X																
Medical History	X																
Physical Exam incl. vital signs 	X																
Targeted PE incl. vital signs 		X	X	X	X	X	X	X	X	X	X	X	X	X	X	X	
ECOG	X	X	X	X	X	X	X	X	X	X	X	X	X	X	X	X	
ECG 	X																
Eligibility Criteria	X																
Concomitant Medications	X	collected at all clinic visits (including atezolizumab dosing visits)															
Adverse Events 	X	collected at all clinic visits (including atezolizumab dosing visits)														X 	
Survival Status and Auto-immune/ IM clinical manifestation																X	
Tumor Biopsy	X 			X 													
Radiology Assessments																	
CT scan: Thorax, Abdomen and Pelvis 	X				X			X	X	X	X	X	X	X	X	X	

Trial Procedure	Screening Phase Day -28 to Day 1	Week (3 wk interval +/- 4 days)						Week (6 wk interval +/- 1 wk)		Week (12 wk interval +/- 2 wks)						Long Term FU	
		1	4	7	10	13	16	22	28	40	52	64	76	88	100 EOT 	3-month interval +/- 2 wks	
		Day															
		1	22	43	64	85	106	148	190	274	358	442	526	610	694 EOT		
		Visit															
		1	2	3	4	5	6	7	8	9	10	11	12	13	14		
Laboratory Assessments																	
Hematology 	X	X	X	X	X	X	X	X	X	X	X	X	X	X	X	X	
Serum Chemistry 	X	X	X	X	X	X	X	X	X	X	X	X	X	X	X	X	
HIV, HbsAg, HCV	X																
INR, PT, aPTT	X																
Thyroid function test	X	X		X		X											
Biomarker Analyses 	X		X		X			X			X						
Urinalysis	X		X		X		X	X	X	X	X	X	X	X	X	X	
Pregnancy Test 	X	X	X	X	X	X	X	X	X	X	X	X	X	X	X	X	
Dosing																	
Prime Vaccine: MVA-BN-CV301 		X	X														
Boost Vaccine: FPV-CV301 				X	X	X	X	X	X	X	X	X	X	X	X	X	
Atezolizumab		X	X	X	X	X	X										

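### The schedule table marks atezolizumab only at Visits 1-6 while the text requires it every 3 weeks through Visit 14, and the plan does not say which window governs the later infusions

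*Protocol*

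**What the plan says.** **The table.** Protocol 4.2 states "This trial will be conducted according to the schedule found in" Section 1.5 for every subject, rules out waivers except for immediate safety concerns, and adds "Visits should be scheduled within the intervals/visit windows given". In that table the row reads "Atezolizumab X X X X X X": marks at Visits 1-6 (Days 1 to 106) and nothing at Visits 7-14. The copy in SAP Section 3 has the same row.

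**The text.** The Protocol synopsis gives "Atezolizumab fixed dose of 1200 mg intravenous on Day 1 of each 21-day cycle", and the SAP General Definitions repeat it. Protocol 4.2.2.2 lists, under Visits 3-14, "Boost vaccinations of FPV-CV301 and atezolizumab infusion", and separately "Atezolizumab dosing visits: Every 3 weeks after Visit 6 through Visit 14". Protocol 8.2.8 refers to 3-weekly visits at which only the infusion is given.

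**The windows.** The table headings give "Week (3 wk interval +/- 4 days" for Visits 1-6, plus or minus 1 week for Visits 7-8, and "Week (12 wk interval +/- 2 wks" for Visits 9-14. Infusion-only visits have no column and no stated window. Neither document states a minimum or maximum interval between infusions. SAP 4.3.1 Table 1 has a column of windows said to be those the protocol allows. It gives Week 22 as Days 144-152, Week 40 as Days 267-281 and Week 52 as Days 351-365.

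**The concern.** The table that sites are told to follow does not show what the text tells them to give. The FPV-CV301 row just above is marked through Visit 14, so the blanks in the atezolizumab row could be taken as meaningful. If sites differed in their reading, atezolizumab exposure after Day 106 would differ by site.

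This matters for interpretation because both null response rates (23% and 15%) are atezolizumab monotherapy rates. Protocol 2.1 describes the study behind the 15% as using dosing every 3 weeks; its account of the 23% study does not restate the schedule. SAP 4.4.7.10 counts doses received but plans no compliance calculation, so a departure from planned dosing would not be reported as such.

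The windows raise a second, smaller question. A tolerance set for 12-weekly visits is attached to visits that are also part of a 21-day cycle, and nothing says whether it applies to the infusion.

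**Working it through.** **Inputs.** Nominal visit days from Protocol 1.5: 1, 22, 43, 64, 85, 106, 148, 190, 274, 358, 442, 526, 610, 694. Cycle length from the synopsis: 21 days. Windows from the Protocol 1.5 headings and SAP Table 1, anchored to nominal days.

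**1. Does the visit calendar fit a 21-day cycle?** (day - 1)/21 is a whole number for all 14 visits. They are infusions 1-6, 8, 10, 14, 18, 22, 26, 30 and 34. The calendar is therefore compatible with dosing every 3 weeks through Visit 14.

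**2. How many infusions are due, and how many are marked?**
- Due from Day 1 through Day 694: (694 - 1)/21 + 1 = 34.
- Marked: 6. Unmarked: 34 - 6 = 28.
- Of the 28, Visits 7-14 account for 8, and 28 - 8 = 20 fall at infusion-only visits with no column.

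**3. How many unmarked infusions precede the response scans?**
- Before the Week 22 scan (Day 148), infusions are due on Days 1 to 127: (127 - 1)/21 + 1 = 7. The table marks 6, so only Day 127 is unmarked.
- Before the Week 28 scan (Day 190): (169 - 1)/21 + 1 = 9 due, 6 marked, 3 unmarked (Days 127, 148, 169). This is the next scheduled scan at which a response first seen at Week 22 could be confirmed.

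**4. What intervals do the protocol windows permit?** Range = 21 plus or minus (window of first infusion + window of second). Infusion-only visits are taken on their nominal days, which is an assumption; the Day 1 window is 0.

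| Where | Sum of windows (days) | Interval (days) | Number of the 33 intervals |
|---|---|---|---|
| Day 1 to Visit 2; Visit 6 to Day 127 | 4 | 17-25 | 2 |
| Between Visits 2 and 6 | 8 | 13-29 | 4 |
| Next to Visits 7-8 | 7 | 14-28 | 4 |
| Next to Visits 9-14 | 14 | 7-35 | 11 |
| Between two infusion-only visits | 0 | 21 | 12 |

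Example: Visit 9 is Day 274 plus or minus 14, that is Days 260-288. The preceding infusion is due on Day 253, so the gap is 260 - 253 = 7 to 288 - 253 = 35 days.

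If infusion-only visits also had plus or minus 4 days (assumed, not stated), the gap next to Visits 9-14 would be 21 plus or minus 18, or 3-39 days. If plus or minus 4 days governed every infusion, including those at shared visits, no gap would fall outside 21 plus or minus 8, or 13-29 days.

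**5. Do the SAP windows match the protocol's?**
- Week 22: Days 144-152 is plus or minus 4 days, against 1 week in the protocol.
- Weeks 40 and 52: Days 267-281 and 351-365 are plus or minus 7 days, against 2 weeks.
- Under the SAP windows, 7-35 days arises only next to the Week 64 to Week 100 visits, 7 of 33 intervals.

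**6. Is the design affected?** No. The stated type I error and power reproduce (0.0244 and 0.7027 for Cohort 1; 0.0249 and 0.7092 for Cohort 2) and do not depend on this point.

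**The case against.** **The blanks may not be in the source.** The thyroid-function row also stops early, at Visit 5, although Protocol 4.2.2.2 and 8.2.7 require the test every 6 weeks through Visit 14. These are two rows whose later frequency does not fit the table's columns, which is what a lost arrow or merged cell would produce. The SAP copy is weak corroboration: as read, its first post-baseline CT mark sits at Visit 3, whereas the protocol has it at Visit 4. Against this, spanning text survived in the adverse-event and concomitant-medication rows, and both copies of the atezolizumab row agree. The possibility stands, and it sets the order of work.

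**The table does not say that dosing stops.** A reader might infer from the blanks that atezolizumab ends at Visit 6. The documents do not support that. The table's adverse-event and medication rows mention atezolizumab dosing visits, footnotes 8 and 10 refer to every infusion, and the text consistently gives a 3-week interval. This objection is right. It leaves a table that disagrees with itself and with the text, not a rule to stop.

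**The windows are not another schedule.** A reader might also infer that infusions 7 days apart comply with the plan, or that 7-35 days applies throughout. Neither follows. A 7-day gap conflicts with the stated 3-weekly dosing, and the range arises in 11 of 33 intervals under an assumption about the neighbouring visit. It can fairly be argued that the plus or minus 4 days in the 3-week heading is the natural window for a 3-weekly infusion. That is plausible, but it is not written for infusion-only or shared visits.

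**Little effect on response.** The Stage 1 decision rests largely on the Week 10 and Week 22 scans, and step 3 shows one unmarked infusion before the second of these. The count of 34 is also a maximum, because Protocol 4.2.5.1 provides for discontinuation at progression. Both points stand. A reader should therefore not take 6 of 34 as the exposure subjects would typically lose, or conclude that the benchmark comparison is invalid.

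**Conclusion.** The point holds as an inconsistency in the operative dosing schedule. As read, the binding table and its SAP copy leave atezolizumab blank at Visits 7-14, where Protocol 4.2.2.2 lists it, and give no column to the infusion-only visits that the table's own rows and footnotes acknowledge. For a subject treated to Day 694, that is 28 of up to 34 infusions not shown. This rests on the blanks being present in the source table.

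The window question does not depend on that. The governing tolerance for an infusion at a shared visit is unstated, no window is given for infusion-only visits, and SAP Table 1 differs from the protocol at Weeks 22, 40 and 52.

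The likely effect on the Stage 1 response rate is small. Responses first seen or confirmed later, duration of response, PFS and the exposure summary are more affected, if sites did in fact read the schedule differently; the documents do not show that they did.

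**What to change.** Check the source table first. If the blanks are real, or if the lost content does not settle the matter:
- reconcile the atezolizumab rows in Protocol 1.5 and SAP Section 3 with the synopsis and Protocol 4.2.2.2, so that all give the same infusion days;
- show in the table the infusion-only visits that the reconciled schedule contains;
- state which window governs the infusion at visits shared with a 6- or 12-weekly vaccination, and what window applies at infusion-only visits;
- align the protocol-allowed windows in SAP Table 1 with the protocol.

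The sponsor's clinical team should set the schedule and the windows; this review takes no view on the values. The cost is a table correction and a footnote in a protocol amendment, with the matching edits in the SAP. No sample-size or analysis change follows.
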